4.6.3.4. Complete blood count, blood chemistry, and urinalysis

Standard complete blood count testing methods shall be used under fasting conditions (8 hours without food). Test material – venous blood, volume drawn – at least 2 mL. This test includes the measurement of the following hematologic parameters:

- Hemoglobin, g/L

Translated from Russian to English, dated 06-Jul-2020

- Red blood cells (cells $\times 10^{12}/L$)
- Platelets (cells $\times 10^9/L$)
- White blood cells (cells $\times 10^9/L$)
- Neutrophils (cells $\times 10^9/L$)
- Lymphocytes (cells $\times 10^9/L$)
- Erythrocyte sedimentation rate (mm/h)

Standard blood chemistry testing methods are used under fasting conditions (8 hours without food, including sweet or alcoholic beverages). Test material – venous blood, volume drawn – at least 4 mL. The test includes determination of the following parameters:

- Total protein (g/L)
- Glucose (mmol/L)
- ALT (U/L)
- AST (U/L)
- Total bilirubin, $\mu\text{mol}/L$
- Creatinine, $\mu\text{mol}/L$

Standard urinalysis shall be performed with assessment of physical, chemical properties and sediment microscopy.

4.6.3.5. Blood test for infection markers

HIV tests include the qualitative assessment of type 1 and 2 anti-HIV antibodies (HIV Ag/Ab Combo) in blood serum or plasma.

Screening syphilis tests include an anti-cardiolipin test (RPR-test) in blood serum.

The presence of hepatitis B infection is assessed based on the results of blood serum or plasma HBsAg testing. The presence of hepatitis C infection is assessed based on total anti-HCV antibody test results.

All the investigations above are conducted in accordance with the standard procedure used at the study site laboratory or central laboratory. Blood volume needed is 6 mL.

Translated from Russian to English, dated 06-Jul-2020

4.6.3.6. Determination of BCD-089, IL-6 receptor, C-reactive protein, IL-6 concentrations

4.6.3.6.1 Determination of BCD-089 concentrations

[Redacted text block]

Table 10. [Redacted]

[Redacted]	[Redacted]

[Redacted text block]

Translated from Russian to English, dated 06-Jul-2020

[REDACTED]

4.6.3.6.2 Determination of Interleukin-6 concentrations

[REDACTED]

Translated from Russian to English, dated 06-Jul-2020

4.6.3.6.3 C-Reactive protein concentration determination

[REDACTED]

Table 12. [REDACTED]

[REDACTED]	[REDACTED]	[REDACTED]	[REDACTED]
[REDACTED]	[REDACTED]	[REDACTED]	[REDACTED]
[REDACTED]	[REDACTED]	[REDACTED]	[REDACTED]
[REDACTED]	[REDACTED]	[REDACTED]	[REDACTED]
[REDACTED]	[REDACTED]	[REDACTED]	[REDACTED]

[REDACTED]

Translated from Russian to English, dated 06-Jul-2020

[REDACTED]

4.6.3.6.4 Determination of soluble IL-6 receptor concentration

[REDACTED]

Table 13. [REDACTED]

[REDACTED]	[REDACTED]
------------	------------

Translated from Russian to English, dated 06-Jul-2020

[Redacted text block]

[figure not shown]
[figure not shown]
4.6.3.8. Receptor occupancy assay

[Redacted text block]

Translated from Russian to English, dated 06-Jul-2020

Figure 9. [Redacted]

4.6.3.9. Chest photofluorography

Chest photofluorography is performed to exclude lung disorders using the method adopted at the study site. If necessary, the Sponsor's representative may request the scans (if active tuberculosis develops during participation in the study).

Translated from Russian to English, dated 06-Jul-2020

4.6.3.10. Electrocardiography

Standard 12-lead ECG is performed.

4.6.3.11. Assessment of injection-related pain by a volunteer

[figure not shown]
The tenderness assessment is performed immediately after the injection or on Day 2 and is performed by a volunteer independently by filling in a special 10-point visual scale (see below) For each injection site (if there were several injections), a separate scale should be filled in to assess the pain.

Figure 10. Point Scale for Pain Assessment

Instruction: this scale reflects how much pain you have experienced during the drug injection. "0" means no pain, "10" - the maximum possible, almost unbearable pain.

4.6.3.12. Assessment of injection site reactions

Injection site reactions are recorded in a separate Injection Site Reaction Registration Form (see Appendix 1). If several injections have been performed, each injection site should be evaluated separately.

4.6.3.13. Technique of performing BCD-089 injections

[Redacted text block]

Translated from Russian to English, dated 06-Jul-2020

[REDACTED]

4.6.3.13. Urine drug test (psychotropic drugs, psychoactive medications)

It is performed once during screening by immunochromatography (using test strips) and is aimed at searching for traces of the use of amphetamine, marijuana, morphine, cocaine (and its metabolites), and methamphetamine. If the test results are positive or doubtful for any of the listed substances, the volunteer must not be included in the study.

Translated from Russian to English, dated 06-Jul-2020

4.6.3.14. Alcohol breath test (quantitative)

The study is performed once at a screening using a certified breathalyzer mentioned in the State register of measuring instruments, with a sensitivity range of 0.00-2.50 mg/mL. If the test results are positive for any of the listed substances, the volunteer must not be included in the study.

4.6.3.15. Unscheduled visits

If adverse events occur, the volunteer may come for an unscheduled visit to conduct additional safety tests which should mandatorily include data collection on concomitant medication, physical examination, BP, body temperature measurements, complete blood count, blood biochemistry, urinalysis, and/or other tests deemed necessary by the Investigator.

4.7. Description of Interruption Rules or Early Withdrawal Criteria for individual subjects, study parts, or the study in general

Volunteers will be excluded from further participation in the study in the following cases:

1. Identification, after the volunteer's inclusion in the study, of gross violations of inclusion/non-inclusion criteria (as decided by JSC BIOCAD)⁵;
2. Patient's withdrawal of the consent to participate in the study;
3. AEs and SAEs, laboratory abnormalities or concomitant diseases, when, in the opinion of the investigator or Sponsor, the continuation of the study treatment is impossible or dangerous for the volunteer, or is not in the best interests of the volunteer, or is unsafe;
4. The volunteer misses more than 1 doses of BCD-089 (in this case, the withdrawal of such a patient will have to be agreed with representatives of JSC BIOCAD);
5. The patient has a major depressive disorder or suicidal ideation or makes suicidal attempts;
6. If the study is terminated by the decision of JSC BIOCAD, local Ethics Committee, or regulatory bodies;
7. In case of the use of drugs prohibited by the Protocol;

⁵Deviations from the eligibility criteria, which are justified by the Investigator and agreed by the Sponsor, are not a reason to exclude the patient from the study.

Translated from Russian to English, dated 06-Jul-2020

8. In case of the volunteer's death.

The Investigator has to inform JSC BIOCAD about the volunteer's premature withdrawal and the reasons of premature withdrawal within 24 hours.

If a volunteer is withdrawn from the study, the Study Completion Form in the CRF must be completed. Follow-up procedures of prematurely withdrawn patients are described in Section 5.4.

See Section 11.5 "Study Termination" below for further details.

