1.2. Name and description (characteristics) of the test drug

1.2.1. Test drug

Trade name: not applicable. Product code: BCD-089.

National nonproprietary name: Anti-interleukin-6 receptor monoclonal antibody

Pharmaceutical form: solution for injection.

Composition per 1 mL:

Active substance: [REDACTED]

Excipients:

[REDACTED]

Manufacturer: JSC BIOCAD, Russia

Shelf life: 2 years.

Storage and transportation conditions:

[REDACTED]

Packaging:

[REDACTED]

Labeling:

In accordance with Article 46 of Federal Law “On the Circulation of Medicinal Products” No. 61-Φ3 of April 12, 2010, the primary packaging of the test drug contains the following Russian text in easily readable font:

Translated from Russian to English, dated 06-Jul-2020

[REDACTED]

[REDACTED]

Manufacturer: JSC BIOCAD, Russia

Shelf life: 2 years.

Storage and transportation conditions:

[REDACTED]

[REDACTED]

Packaging:

[REDACTED]

[REDACTED]

[REDACTED]

Labeling:

In accordance with Article 46 of Federal Law “On the Circulation of Medicinal Products” No. 61-Φ3 of April 12, 2010, the primary packaging of the test drug contains the following Russian text in easily readable font:

- “Diluent”,
- batch number,
- release date,
- expiry date,
- volume.

The secondary packaging contains the following information in Russian in easily readable font:

- name: “Diluent”,
- manufacturer name: JSC BIOCAD, Russia,
- batch number,
- release date,
- expiry date,
- method of administration,
- volume,
- storage conditions,

Translated from Russian to English, dated 06-Jul-2020

- cautionary information.

Primary and secondary packaging of the test drug will be additionally labeled with: “For clinical studies only”.

Method of administration and dosing regimen:

In this study, the drug will be administered as a single-dose subcutaneously. The administered dose of BCD-089 depends on the cohort into which the volunteer was assigned:

1. Cohort 01 - 1 volunteer to whom a single subcutaneous injection of BCD-089 at a dose of 0.06 mg/kg will be administered.
2. Cohort 02 - a maximum of 6 volunteers to whom a single subcutaneous injection of BCD-089 at a dose of 0.3 mg/kg will be administered.
3. Cohort 03 - a maximum of 6 volunteers to whom a single subcutaneous injection of BCD-089 at a dose of 0.625 mg/kg will be administered.
4. Cohort 04 - a maximum of 6 volunteers to whom a single subcutaneous injection of BCD-089 at a dose of 1.0 mg/kg will be administered.

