4.2 Design

Clinical study No. BCD-089-1 is a classic open-label, single-center, non-randomized cohort clinical study of the pharmacokinetics, pharmacodynamics, tolerability and safety of a novel drug in healthy volunteers at increasing doses (phase 1, 3+3 design).

Before being included in the study, healthy volunteers have to sign a written informed consent after having read it, after which they will undergo a 14-day screening examination to confirm compliance with the eligibility criteria for the study. No additional requirements regarding a certain diet or restriction of physical activity, both during the screening period and throughout the study, are specified in this protocol.

Study No. BCD-089-1 includes seven cohorts:

1. Cohort 01 - 1 volunteer to whom a single subcutaneous injection of BCD-089 at a dose of 0.06 mg/kg will be administered.
2. Cohort 02 - a maximum of 6 volunteers to whom a single subcutaneous injection of BCD-089 at a dose of 0.3 mg/kg will be administered.
3. Cohort 03 - a maximum of 6 volunteers to whom a single subcutaneous injection of BCD-089 at a dose of 0.625 mg/kg will be administered.

Translated from Russian to English, dated 06-Jul-2020

4. Cohort 04 - a maximum of 6 volunteers to whom a single subcutaneous injection of BCD-089 at a dose of 1.0 mg/kg will be administered.
5. Cohort 05 - a maximum of 6 volunteers to whom a single subcutaneous injection of BCD-089 at a dose of 1.6 mg/kg will be administered.
6. Cohort 06 - a maximum of 6 volunteers to whom a single subcutaneous injection of BCD-089 at a dose of 2.2 mg/kg will be administered.
7. Cohort 07 - a maximum of 6 volunteers to whom a single subcutaneous injection of BCD-089 at a dose of 2.9 mg/kg will be administered.

***Note.** If a volunteer is administered 1 mL of the solution and, therefore, it is necessary to perform two injections to administer the calculated dose, it is preferable to administer the drug to the same anatomical region, provided that the site of the subsequent injection is no closer than 5 cm from the previous one. The duration of administering several injections should not exceed 10 minutes; calculation of time for PK sampling starts from the “last” drug injection.

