5.3. Exclusion criteria

Volunteers will be excluded from further participation in the study in the following cases:

1. Identification, after the volunteer's inclusion in the study, of gross violations of inclusion/non-inclusion criteria (as decided by JSC BIOCAD);
2. Patient's withdrawal of the consent to participate in the study;
3. AEs and SAEs, laboratory abnormalities or concomitant diseases, when, in the opinion of the investigator or Sponsor, the continuation of the study treatment is impossible or dangerous for the volunteer, or is not in the best interests of the volunteer, or is unsafe;
4. The volunteer misses more than 1 doses of BCD-089 (in this case, the withdrawal of such a patient will have to be agreed with representatives of JSC BIOCAD);
5. The patient has a major depressive disorder or suicidal ideation or makes suicidal attempts;
6. If the study is terminated by the decision of JSC BIOCAD, local Ethics Committee, or regulatory bodies;
7. In case of the use of drugs prohibited by the Protocol;
8. In case of the volunteer's death.

Translated from Russian to English, dated 06-Jul-2020

The investigator had to inform JSC BIOCAD about his premature withdrawal and the reasons of premature withdrawal within 24 hours.

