5.3.1. Substitution of volunteers who withdrew from the study

The volunteers can be substituted in the following cases:

1. Volunteers who withdrew the study for reasons not related to administration of the study drug (missing visit, withdrawal of consent, systematic violation of visit windows, etc.).
2. Non-compliant volunteers (see Section 6.6).

Volunteers who withdrew from the study after administration of the study drug for safety reasons (AE that did not allow to come to a visit to perform the Protocol procedures) will not be replaced.

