5.4. Follow-up of subjects who withdrew from the study

Follow-up of volunteers who received at least one dose of the drug

In case of early withdrawal of a volunteer after administration of the study drug, it is required to conduct an “Early Withdrawal Visit” and fill out an “Early Withdrawal Form”.

If a patient is discontinued from the study due to an AE/SAE, the Investigator should continue his/her management and follow-up after the “Early Withdrawal Visit” in accordance with the standard practices used at the study site for AE/SAE treatment. The volunteer will be followed up until full resolution of the AE or SAE.

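### After the single injection, withdrawal criterion 3 stops no treatment but ends scheduled sampling, and can cost a volunteer his PK, PD and immunogenicity data

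*Combined protocol and SAP*

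**What the plan says.** Section 1.2.1 sets the regimen: "In this study, the drug will be administered as a single-dose subcutaneously". The one complication is the note in section 4.2, which covers the case where "it is necessary to perform two injections to administer the calculated dose", within 10 minutes.

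Sections 4.7 and 5.3 carry the same eight-item list under the same lead-in: "Volunteers will be excluded from further participation in the study in the following cases". Criterion 3 covers AEs, laboratory abnormalities and concomitant diseases for which, in the view of the investigator or sponsor, "continuation of the study treatment is impossible or dangerous for the volunteer, or is not in the best interests of the volunteer, or is unsafe". Criterion 7 reads "In case of the use of drugs prohibited by the Protocol".

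Section 5.4 deals with what follows: "In case of early withdrawal of a volunteer after administration of the study drug, it is required to conduct an" Early Withdrawal Visit. For a volunteer discontinued because of an AE or SAE it adds: "The volunteer will be followed up until full resolution of the AE or SAE". The visible text does not continue PK, PD or antibody sampling. The visit descriptions (4.6.2) and the missing-data section (9.5) are blacked out.

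Section 5.3.1 does not replace post-dose safety withdrawals, which it explains as an "AE that did not allow to come to a visit to perform the Protocol procedures". It allows replacement when the reason is unrelated to the drug. Section 9.7 keeps a volunteer in the PK set, and separately in the PD set, with at most two missing samples; the immunogenicity set requires both the Day 1 and the Day 71 samples. Section 6.6 also draws its line at more than two missed samples. Section 11.2 lists two or more as a probable major deviation, and a major deviation removes the volunteer from the final PK/PD analysis.

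**The concern.** Criterion 3 asks a question about treatment and answers it by ending study participation. In a multi-dose trial the two are linked. Here, once dosing is complete, there is nothing left to stop. The practical effect of applying the criterion is to end the scheduled visits.

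The volunteers concerned are those with an adverse event, an abnormal laboratory value or a new illness after exposure. Their later concentrations, PD markers and Day 71 antibody result help to interpret the event. In a first-in-human study with cohorts of 3 to 6 (one in cohort 01), each profile matters. The visits that would supply these data are already in the schedule.

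**Working it through.** **Cohort sizes.** The sample-size table gives 1 + 6 × (3 + 3) = 37, which agrees with the stated maximum of 37. Without expansion for a DLT the total is 1 + 6 × 3 = 19, so three is the usual cohort size.

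**Sampling grid.** Sections 9.1.1 and 9.1.2 give the same 16 times for PK and PD, in hours: 0, 2, 8, 12, 24, 48, 72, 96, 120, 168, 240, 336, 504, 672, 1176, 1680. By Table 9 the last four fall on Days 22, 29, 50 and 71.

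**Missing samples.** The number missing equals the number of planned times after the last sample taken. The right-hand count assumes that the redacted text provides one sample at the withdrawal visit and that it counts as one of the 16.

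| Last scheduled sample | Missing, visible text | PK/PD sets (9.7) | Missing, one withdrawal sample counted | PK/PD sets (9.7) |
|---|---|---|---|---|
| Day 2 (24 h) | 11 | out | 10 | out |
| Day 8 (168 h) | 6 | out | 5 | out |
| Day 11 (240 h) | 5 | out | 4 | out |
| Day 15 (336 h) | 4 | out | 3 | out |
| Day 22 (504 h) | 3 | out | 2 | in |
| Day 29 (672 h) | 2 | in | 1 | in |
| Day 50 (1176 h) | 1 | in | 0 | in |

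- On the visible text, exit before the 672 h sample loses the PK and PD sets: 672/1680 = 40% of follow-up.
- With one withdrawal-visit sample counted, exit before the 504 h sample does so: 504/1680 = 30%.
- For immunogenicity, section 9.7 names Day 71, so exit at any time before that sample loses the set. A sample drawn earlier is not the Day 71 sample.

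**Share of a cohort.** One exit that is not replaced costs 1/3 = 33% of the profiles in a cohort of three, or 1/6 = 17% after expansion. In cohort 01 it costs the only profile.

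**Conflict over exactly two missing.** Exit between the Day 29 and Day 50 samples, (1176 − 672)/1680 = 30% of follow-up, leaves exactly two missing on the visible text. Sections 9.7 and 6.6 accept this. Section 11.2 lists it as a probable major deviation, if samples not drawn after a protocol-required withdrawal count as missing there.

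**The case against.** The strongest reply is that criterion 3, read literally, cannot be met after the only injection. On that view it is leftover multi-dose wording, like criterion 4 on missed doses, and harms nobody. This does not dispose of the point. Section 5.3.1 provides for safety withdrawals after administration, section 5.4 provides for discontinuation due to an AE or SAE, and section 4.1.4 makes AE-related discontinuation a per-cohort endpoint. The plan expects such exits, and criterion 3 is the listed ground that mentions AEs.

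Four stronger readings are tempting, and the documents do not support them.

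- *A reader might infer that any AE removes a volunteer.* It does not; criterion 3 needs a judgement by the investigator or sponsor. Before the injection, or between two split injections, its wording also has a real object.
- *A reader might infer that criterion 7 has the same defect.* It is not tied to treatment. Section 6.4 bars additional medicines in general but sets no specific restriction for intercurrent illness, so the criterion's reach is unclear. Section 11.2 lists prohibited medication as a probable major deviation, so PK/PD data may be excluded even if the volunteer stays.
- *A reader might take 33% as the expected loss.* It is the most that one exit can cost in a cohort of three. Criterion 3 also covers concomitant disease, and an exit unrelated to the drug can be replaced. Section 5.3.1 does not say how it treats a safety exit by a volunteer who could still attend.
- *A reader might infer that dose escalation or the safety analysis is compromised.* The safety set keeps every dosed volunteer, and nothing shows an effect on the 7-day DLT count. Section 4.6.3.15 also allows unscheduled visits with further tests for an AE, and 5.4 follows the event to resolution. These help in managing the event, but they do not restore eligibility under 9.7.

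The redactions are a fair limit: 4.6.2 or 9.5 may provide a withdrawal-visit sample or a missing-data rule. That is why the PK/PD boundary is given as a range.

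**Conclusion.** The point stands for criterion 3. If it is applied after the injection, it ends scheduled sampling without stopping any treatment. The PK and PD sets are lost for an exit before the Day 29 sample on the visible text, or before the Day 22 sample if one withdrawal-visit sample counts. The immunogenicity set is lost for any exit before the Day 71 sample. The cost per exit is at most one of three profiles in an unexpanded cohort of three.

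Criterion 7 is secondary. Keeping such a volunteer mainly gains safety follow-up and the Day 71 antibody result.

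The conclusion assumes that withdrawal ends the scheduled draws, as the visible text of 5.4 implies, and that no redacted rule lets another sample stand in for Day 71. The documents give no withdrawal rate and no link between exposure and AEs, so the size of any bias cannot be estimated. This is a low-to-moderate priority change, worth making because it needs only wording.

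**What to change.** 1. In 4.7 and 5.3, state that a dosed volunteer who meets criterion 3 or 7 stays in scheduled safety, PK, PD and Day 71 sampling unless he withdraws consent or the visits or blood draws themselves (not the treatment) are judged unsafe. For consistency, apply the same rule to criteria 1 (eligibility violation) and 5 (depression or suicidality) where it is safe.
2. Flag samples taken under other medication and run a sensitivity analysis on them.
3. State that the endpoint on AE-related discontinuation still counts volunteers who meet criterion 3, even if they remain in follow-up. Otherwise the change alters what the endpoint measures.
4. In 11.2, change the limit from two or more to more than two missing samples, to match 9.7 and 6.6.

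Deleting criterion 4, which cannot occur with one dose, is tidying only.

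The cost is protocol wording; the visits and samples are already scheduled. The downside is that some profiles will include samples taken under other medication. Samples missed because an AE prevents attendance are not recovered, and some loss at the investigator's discretion remains. For criterion 7, section 11.2 may still exclude the PK/PD data.

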4.8. Drug accountability procedures used in the study

The Investigator is responsible for study drug accountability. The Investigator must keep accurate records of the drugs throughout the study, in compliance with regulatory requirements. The Investigator must document the supply of drugs from JSC BIOCAD.

When the Investigator or a pharmacist receives the drugs, he/she must check the received lot, sign and date the form of drug supply and the documentation provided by JSC BIOCAD, and then return it to JSC BIOCAD. Copies of these documents must be stored in the Investigator's File.

The amount of supplied drugs must be recorded in the Drug Accountability Form provided by JSC BIOCAD, which then may be used as a balance sheet for the investigational product.

Accurate accountability records must be made available to the monitor for verification at each monitoring visit. Drug accountability records must include:

- Confirmation of supply to the study site;
- Inventory at the study site;
- Use of drugs by each study subject;
- Return to JSC BIOCAD of unused products.

Records must also include the date, amount, batch number, lot number and expiry date (if applicable). The Investigator must keep records to ensure that:

- The study participants must be provided with the doses established by the Protocol/amendment;
- All the investigational products supplied by JSC BIOCAD was fully checked, delivered in full and undamaged.

Any unused investigational product must be restricted from use for any other purposes outside this study.

Translated from Russian to English, dated 06-Jul-2020

A monitor of JSC BIOCAD will collect drug accountability reports on a regular basis.

